2. BACKGROUND

2.1 Prostate Cancer

Due to widespread screening with the prostate-specific antigen (PSA) assay, prostate cancer is the most frequently diagnosed non-cutaneous cancer among U.S. men. While prostate cancer mortality has declined during the screening era, this has occurred at the cost of substantial over diagnosis and overtreatment, unnecessarily exposing many patients to side effects of therapy, such as erectile dysfunction, urinary incontinence, and proctitis [1, 2].

Population studies suggest that a substantial proportion of men diagnosed with localized prostate cancer in the US are over-treated [3-5]. This public health problem—unnecessarily aggressive treatment of tens of thousands of men each year who subsequently suffer chronic side effects—challenges us to develop innovative therapeutic models to refine treatment paradigms within this patient population.

In recent years, active surveillance has increasingly garnered attention as an alternative, and less morbid, approach to surgery or radiation in men with clinically localized, low-risk prostate cancer. Follow-up

assessments in patients on active surveillance include serial PSA measures, repeat prostate biopsy and, increasingly, prostate MRI. Most men on active surveillance followed for up to 15 years will not require treatment. However, up to one-third of active surveillance patients will undergo treatment within 2 to 5 years of initiating surveillance [6].

Development of intervention strategies to prevent disease progression in patients on active surveillance thus represents an important area of prostate cancer chemoprevention. Prior studies have yielded promising early results. The Prostate Cancer Lifestyle Trial compared intensive dietary and lifestyle modifications for men on active surveillance to usual care and reported a significantly lower rate of secondary treatment for the intervention arm after 2 years of follow-up [7]. The Reduction by Dutasteride of Clinical Progression Events in Expectant Management (REDEEM) trial assessed the efficacy of dutasteride in preventing disease progression in active surveillance patients. After 3 years, 38% and 48% of the dutasteride and control participants, respectively, had progressed by pathologic or therapeutic criteria, a relative risk reduction of 21% for dutasteride [8]. An ongoing multicenter study is evaluating whether a dietary intervention could delay disease progression in men on active surveillance [9].

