Participants will return for the post-intervention visit 7-14 days after the last scheduled dose of vaccine. Blood will be collected prior to the biopsy procedure for CBC-diff, CMP, PSA, PBMCs, and serum. Participants will be evaluated for weight, vital signs, AEs and concomitant medications. International Prostate Symptom Score will be obtained. DRE will be performed at the discretion of the individual urologist. TRUS-guided prostate biopsy or targeted prostate biopsy using MR-US fusion will be performed as part of the routine care of patients on active surveillance. The results of all PSA tests performed during the intervention will be collected. Pre- and post-intervention biopsy pathology reports will be collected and submitted to the University of Arizona Early Phase Chemoprevention Consortium Office. Unstained slides from the pre- and post-intervention prostate biopsies will be requested from the institutional pathology lab for analysis of the change in immune infiltrates in the target tissue.

If available, reports from the prostate MRI scans performed (and companion pathology reports) from 3 years prior to and 6 months after the study intervention will be collected and submitted to the University of Arizona Early Phase Chemoprevention Consortium Office to capture the lesion size information.

Study subjects will be followed for 30 days after the last study dose is given. Participants will continue to record adverse events during the follow-up period. The diary will be mailed back to the study staff in a pre-addressed, stamped envelope. Study staff will contact the subject by phone, if necessary, to clarify any of the diary entries.

Participants will return for a follow-up visit 6 months after the post-intervention biopsy or 6 months after the last study dose is given, if no post-intervention biopsy was performed, as part of the standard-of-care. Blood will be collected for PSA. International Prostate Symptom Score, interval medical history, and documentation on whether participant is still on active surveillance will be obtained. DRE will be performed at the discretion of the individual urologist. Patients who have undergone prostatectomy, radiation therapy or focal prostate cancer therapy are exempt from the six-month follow-up visit requirement.

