4. PARTICIPANT SELECTION

4.1 Inclusion Criteria

- 4.1.1 Biopsy-proven (consisting of ≥ 10 tissue cores) adenocarcinoma of the prostate with cancer present in at least one biopsy core, either random or targeted, in the most recent biopsy.
- 4.1.2 All prior biopsies must meet the following: $\leq 50\%$ of the total number of random biopsy cores positive for cancer
 - Gleason score $\leq (3+4)$
- 4.1.3 Clinical stage $\leq T2a$ by DRE
- 4.1.4 Biopsies performed at outside institutions should have Gleason score confirmed at the study site by a GU pathologist to ensure eligibility.
- 4.1.5 Pre-intervention biopsy tissue (most proximal to enrollment) containing sufficient tumor tissue to cut 5-10 unstained slides confirmed to be available upon request.
- 4.1.6 Screening serum PSA < 20 ng/mL. For men treated with 5-alpha-reductase inhibitors (e.g., finasteride, dutasteride), PSA needs to be < 10 ng/mL.
- 4.1.7 Hematological eligibility parameters:
Neutrophil count $\geq 1,200/\text{mm}^3$ (≥ 1.2 k/ μL)
Stable platelet count $\geq 75,000/\text{mm}^3$ (≥ 75 k/ μL)
- 4.1.8 Hepatic and renal function eligibility parameters:
Bilirubin ≤ 1.5 mg/dL (or ≤ 3.0 mg/dL for patients with Gilbert's syndrome)
ALT and AST ≤ 2.5 x ULN
Serum creatinine ≤ 1.5 x ULN
- 4.1.9 Karnofsky $\geq 70\%$; see Appendix A.
- 4.1.10 Must agree to use medically acceptable barrier and/or chemical method of contraception while on study and for at least one month following the last vaccine injection because the effects of PROSTVAC® on the developing human fetus at the recommended therapeutic dose are unknown. Should a participant's partner become pregnant or suspect she is pregnant while the participant is participating in this study, the study physician should be informed immediately. In the event a participant's partner becomes pregnant, the study sponsor may request additional information regarding the course of the pregnancy and if the pregnancy is carried to term, the birth of the child (i.e., the outcome of the pregnancy).
- 4.1.11 Ability to understand and the willingness to sign a written informed consent document.
- 4.1.12 No planned prostate biopsies during the intervention until after the post-intervention biopsy.
- 4.1.13 Men on stable doses of 5-alpha reductase inhibitors are eligible as long as there is no planned dose change while on study.

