7.4 Evaluation at Completion of Study Intervention

Seven to fourteen days after the last scheduled vaccine dose, participants will return for the post-intervention visit. Blood will be collected for CBC-diff, CMP, PSA, PBMCs, and serum prior to the digital rectal exam and collection of the post-intervention biopsy. Participants will be evaluated for weight, vital signs, AEs and concomitant medications. International Prostate Symptom Score will be obtained. DRE will be performed at the discretion of the individual urologist. TRUS-guided prostate biopsy or targeted prostate biopsy using MR-US fusion will be performed as part of the routine care of patients on active surveillance.

Pre- and post-intervention biopsy pathology reports will be collected, de-identified, labeled with study ID and participant ID and submitted to the University of Arizona Early Phase Chemoprevention Consortium Office.

Report Submission Information:
University of Arizona Early Phase Chemoprevention Consortium Office
Attn: [name]
[name]
[name]
[contact]
[contact]
Email: [contact]

Unstained tissue slides from the pre- and post-intervention prostate biopsies will be requested from the institutional pathology lab for analysis of the immunologic response in the target tissue.

If available, reports from the prostate MRI scans (and companion pathology reports) performed from 3 years prior to and 6 months after the study intervention will be collected. Reports will be de-identified, labeled with study ID and participant ID and submitted to the University of Arizona Early Phase Chemoprevention Consortium Office to capture the lesion size information.

The results of all PSA tests performed throughout the intervention as part of the routine care of patients on active surveillance will be collected.

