8.2 Secondary Endpoints

- 8.2.1 To assess the effect of PROSTVAC® on the change in PD-L1 positive cells in the stroma adjacent to tumor and within the malignant portion of the prostate biopsies. The change will be compared between participants treated with PROSTVAC® and those treated with placebo. A subgroup analysis will be performed to compare the change in PD-L1 positive cells between study groups in specimens collected by targeted biopsy.
- 8.2.2 To assess the correlation between the change in CD8⁺ and the change in PSA. The correlation between the change in CD8⁺ in the stroma adjacent to tumor and within the malignant portion of the prostate biopsies and the change in PSA (from baseline to 6 months (5-7 months) post-intervention) in participants treated with PROSTVAC® will be examined.
- 8.2.3 To assess the effect of PROSTVAC® on the change in CD8⁺, CD4⁺, and PD-L1 positive cells in the benign portion of the prostate biopsies. The change will be compared between participants treated with PROSTVAC® and those treated with placebo.
- 8.2.4 To assess the effect of PROSTVAC® on the change in PSA. The change in PSA from baseline to 6 months (5-7 months) post-intervention will be compared between participants treated with PROSTVAC® and those treated with placebo.
- 8.2.5 To assess the effect of PROSTVAC® on tumor grade progression, defined as a post-intervention

- Gleason score of $\geq 4+3$ using all biopsy data, i.e., from random and target biopsy cores. Proportion of men with post-intervention Gleason score of $\geq 4+3$ will be compared between the treatment groups. In addition, this endpoint will be evaluated in the subgroup of patients in whom MRI-targeted biopsies were obtained pre- and post-intervention.
- 8.2.6 To assess the effect of PROSTVAC on tumor extent based on the percent of positive random biopsy cores. The change in tumor extent will be compared between the treatment groups.
 - 8.2.7 To assess the proportion of men with no cancer in the post-intervention biopsy between participants treated with PROSTVAC® and those treated with placebo. This analysis will utilize all biopsy data, i.e., from random and target biopsy cores.
 - 8.2.8 To assess the effect of PROSTVAC on the size of the dominant lesion on MRI (largest histopathologically confirmed lesion) in the subgroup of patients with MRIs pre and post-intervention.

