13. STATISTICAL CONSIDERATIONS

13.1 Study Design/Description

This study utilizes a Phase II double-blind, randomized, placebo controlled design to assess the effect of PROSTVAC® in patients with clinically localized prostate cancer undergoing active surveillance. Each eligible participant will be randomly assigned to receive either PROSTVAC® or matched placebo. Due to potential withdrawals and the absence of tumor in the post-intervention biopsy, 25% or more participants may not provide endpoint data. All of the statistical analysis (both primary and secondary analysis) will be based on the intent-to-treat principle. Multiple imputation (MI) techniques will be applied, as necessary, for participants without endpoint data. The statistical analysis based on Rubin's rules will be performed on the imputed datasets, if MI is performed.

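### Grade progression is scored only on the post-intervention biopsy, so a man upgraded on an unplanned biopsy and treated before it is not counted as progressed

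*Combined protocol and SAP*

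**What the plan says.** - **Endpoint.** Section 8.2.5 compares the "Proportion of men with post-intervention Gleason score of" 4+3 or higher between arms, "using all biopsy data, i.e., from random and target biopsy cores". Section 13.5 describes the same endpoint as an increase to that level and tests it with Fisher's exact test. The two descriptions agree, because 4.1.2 admits only men whose prior biopsies were at most 3+4. Section 8.2.7 likewise ties absence of cancer to the post-intervention biopsy.
- **Timing.** Section 3: "Participants will return for the post-intervention visit 7-14 days after the last scheduled dose of vaccine". With the last booster at Day 140, this is nominally Day 147-154.
- **Earlier biopsies.** Criterion 4.1.12 reads "No planned prostate biopsies during the intervention until after the post-intervention biopsy". Unplanned biopsies are not addressed.
- **Reports collected.** Section 7.4: "Pre- and post-intervention biopsy pathology reports will be collected". The Schedule of Events requests biopsy reports only at screening and post-intervention. Sections 3 and 7.4 also seek MRI reports with their companion pathology, where available, from 3 years before to 6 months after the intervention.
- **Men without the biopsy.** Section 3 sets their follow-up visit at "6 months after the last study dose is given, if no post-intervention biopsy was performed". Sections 3 and 7.5 excuse men who have had prostatectomy, radiation or focal therapy from that visit. Neither provision says how such men enter the endpoint.
- **Missing data.** Section 13.1: "Multiple imputation (MI) techniques will be applied, as necessary, for participants without endpoint data". Section 13.5 repeats this for the secondary endpoints.

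**The concern.** The plan recognises that some men will have no post-intervention biopsy and that some will be treated, but it gives no endpoint rule for a man to whom both apply. If an unplanned biopsy shows 4+3 or higher and he is treated before Day 147, he has met the substance of the endpoint, yet he enters the analysis as missing. He is missing because he progressed. Imputing him from men biopsied on schedule gives him something near their risk, and leaving him out removes an event. In 8.2.7 he could be imputed as cancer-free although cancer was found on study.

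Clinical indicators of progression are part of the overall objective in Section 1, and delay of progression is the hypothesis in Section 2.3. With few events expected, the scoring of a handful of men can matter. If it is settled after unblinding, the choice could shape the result.

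**Working it through.** **1. Does any other provision count this man?** Set side by side:
- 8.2.5 requires a post-intervention score from biopsy cores.
- 8.3 promises continued collection of endpoint data, but according to the Schedule of Events, which requests no interim biopsy report.
- 8.3 and 8.4 name neither progression nor definitive treatment as a reason for stopping agent or leaving the study.
- 13.4 and 13.5 provide for imputation using predictors of missingness, but no section requires the early pathology to be collected.

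None closes the gap.

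**2. How many men can be affected?** Inputs from 13.4: 150 randomized as 100 and 50, 10% attrition, 70% of biopsies with tumor.
- The plan's evaluable numbers: 100 x 0.90 x 0.70 = 63 and 50 x 0.90 x 0.70 = 31.5 (stated as 63 and 31). They reproduce, but belong to the primary endpoint.
- Men with no post-intervention biopsy: 100 x 0.10 = 10 and 50 x 0.10 = 5, so 15 of 150. This is a projection for all causes, including withdrawal and refusal. The figure of 25% or more in 13.1 also includes men biopsied without tumor, who are not at issue here.

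**3. A rough external ceiling.** Section 2.1 says that "up to one-third of active surveillance patients will undergo treatment within 2 to 5 years of initiating surveillance". Read as a constant hazard over 154 days (about 5.06 months):
- one-third in 24 months: -ln(2/3)/24 = 0.0169 per month; 1 - exp(-0.0169 x 5.06) = 8.2%, about 12 of 150;
- one-third in 60 months: -ln(2/3)/60 = 0.00676 per month; 1 - exp(-0.00676 x 5.06) = 3.4%, about 5 of 150.

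These are men treated for any reason, and the source figure is itself an upper one. The hazard is probably lower over an interval with no planned biopsy.

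**4. Effect on the comparison (illustration).** The documents give no progression rate. Assume 5% (PROSTVAC) v 15% (placebo) among biopsied men. Imputation at the observed arm rates, or exclusion, leaves the difference at -10.0 points. If e men in an arm of n were upgraded early and are counted, and everyone else has the arm's rate p, the proportion is [(n - e)p + e]/n.

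| Early upgrades, PROSTVAC v placebo | Proportions | Difference (points) |
|---|---|---|
| 1 v 1 | 5.95% v 16.7% | -10.75 |
| 2 v 1 | 6.9% v 16.7% | -9.8 |
| 1 v 3 | 5.95% v 20.1% | -14.15 |
| 0 v 5 | 5.0% v 23.5% | -18.5 |
| 10 v 5 (all projected attrition) | 14.5% v 23.5% | -9.0 |

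For example, placebo with 3: (47 x 0.15 + 3)/50 = 20.1%. With 5% in both arms, 2 v 1 leaves the difference at 0 (6.9% v 6.9%), and the extreme 0 v 5 moves it to -9.5 (5.0% v 14.5%).

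Losses in proportion to the 2:1 allocation hardly move the difference; unbalanced losses do.

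**The case against.** The strongest reply is that the scenario is conjectural. The documents never mention for-cause biopsies, none is planned, and the interval is about five months. Grade is item 1.2.5 of a prioritized list, below PSA change, 13.5 calls the secondary analyses exploratory, and no power is claimed for it. Section 13.5 also reports and compares missing rates by arm and models missingness, and variables such as the Day 84 PSA could enter the imputation. All of this stands and limits the size. It does not supply the missing rule, and a model using PSA does not recover a grade already on a pathology report.

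One could also say that the reference to all biopsy data in 8.2.5 already covers an unplanned biopsy. The text explains that phrase as random and target cores, and the score must still be post-intervention. The post-intervention column of the Schedule of Events refers to the last dose without the word scheduled, so a site might file an early biopsy as the endpoint biopsy for a man who stopped injections. That would be a local decision, not a rule.

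Scoring a single scheduled biopsy is a legitimate choice because it keeps timing uniform, and an upgrade found soon after Day 0 may be disease missed at entry. Both are reasons to keep the scheduled-biopsy definition as a sensitivity analysis. Randomization should balance disease missed at entry on average.

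A reader might infer that any upgrade at surgery is lost. The documents do not support that: a man operated on after the endpoint biopsy is scored on that biopsy. Needle and surgical grades are also not fully interchangeable, so surgical pathology does not belong in the main analysis.

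**Conclusion.** The gap is real and its likely effect is small. A man with Gleason 4+3 or higher proven on an unplanned biopsy, and treated before the endpoint biopsy, is imputed or left out, and in neither case counted as progressed. The plan's projection limits all men without a biopsy to about 15 of 150, and those upgraded early are an unknown part of them. The difference between arms moves materially only if early upgrades are unbalanced. The progression rates and early-upgrade counts in the illustration are assumptions.

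Three stronger readings are not supported:
- A reader might infer that a large share of true events is lost. Assuming 8% upgraded on schedule and half of 5-12 treated men upgraded would give about 18-35% of events, but this multiplies an upper bound by two inputs that the documents do not contain.
- A reader might infer a known direction of bias, including that harm is understated if the vaccine does not delay progression. With no effect, losses should be roughly balanced. A benefit is understated if placebo men are upgraded early disproportionately often, and harm only if vaccine men are.
- A reader might take this as the trial's main clinical indicator of progression. No section says so.

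**What to change.** Before unblinding:
- **8.2.5 and 13.5:** for a man with no post-intervention biopsy, count Gleason 4+3 or higher on any prostate biopsy from Day 0 through the post-intervention biopsy window as grade progression. Use multiple imputation only for men with no on-study prostate histology (in the main analysis, biopsy histology).
- **7.4 and the Schedule of Events:** collect the reports of those biopsies.
- **Sensitivity analyses:** report the scheduled-biopsy-only definition. In a further analysis, add surgical pathology obtained before the endpoint biopsy, after checking that the records release covers it.
- **8.2.7:** do not impute as cancer-free a man who has no post-intervention biopsy but has cancer on an on-study biopsy. Never override an observed post-intervention biopsy.

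The cost is a protocol amendment and a few extra pathology reports, some of which may already arrive as MRI companion pathology. The release described in Sections 3 and 7.2 names biopsy pathology reports but not surgical ones. The downside is a biopsy date that is not uniform for these men. Treatment, visits and sample size do not change.
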